7.3. Efficacy Derived Variables

7.3.1. WI-NRS

The WI-NRS is a PRO instrument, designed to quantify the intensity of worst itching experienced during a 24-hour period. The scale is a set of boxes, one for each number, from 0 (no itching) to 10 (worst possible itching). The NRS is a widely used instrument recommended by the IFSI for quantifying itch intensity as well as a useful instrument for grouping subjects into categories of itch intensity described as mild, moderate, or severe³: The itch NRS has been investigated in subjects with chronic pruritus of a variety of origins, and a high reliability and concurrent validity was found^{3,4}.

In this study, during the double-blind period, subjects will be asked to record the WI-NRS value daily, at approximately the same time each day, usually in the late afternoon or early evening. All WI-NRS information will be entered into the e-diary. During the open-label period, only a single value will be collected for the WI-NRS at each study visit. This will be collected using the same electronic diary format via web portal.

The primary endpoint depends on the change from baseline to Week 14. The calculation of the Week 14 value is described below.

For the 2-, 6- and 10-week visits, the WI-NRS will be calculated as the arithmetic means of the WI-NRS values on Study Days 8 through 14 (Week 2), 36 through 42 (Week 6), and 64 through 70 (Week 10), respectively, regardless of when the Weeks 2, 6 and 10 visits actually occur.

The Week 14 WI-NRS is calculated as follows:

- Case 1: Subject's Week 14 visit is on or after Study Day 98 (target day)
 - Use all values in the period Study Day 92 through Study Day 98
 - If there are ≥ 5 values, calculate the arithmetic mean of them
 - If there are < 5 values, calculate an arithmetic mean based on all of them plus any available values in the range from Study Day 99 till titration begins that will bring the total to 5 values, but do not use any values collected after titration begins. If this range has more values than necessary to bring the total to 5 values, use values closest to Study Day 98. If there are still less than 5 values, continue to use any available values in the first 3

days before Day 92 that will bring the total to 5 values. If this range has more values than necessary to bring the total to 5 values, use values closest to Study Day 92

- Case 2: Subject's Week 14 visit is before Study Day 98
 - Use all values from Study Day 92 to the Study Day of the Week 14 visit
 - If there are ≥ 5 values, calculate the arithmetic mean of them
 - If there are < 5 values, calculate an arithmetic mean based on all of them plus any available values in the first 3 days before Day 92 that will bring the total to 5 values. If this range has more values than necessary to bring the total to 5 values, use values closest to Study Day 92

A "Responder" is defined as a subject with a ≥ 4 -point decrease in the 7-day average WI-NRS from baseline to Week 14. Baseline is as described in [Section 7.2.1](#).

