The following procedures will be performed during this visit:

- Physical examination
- Brief neurological assessment
- Vital signs
- Clinical laboratory assessments
- Urine pregnancy test (WOCBP)
- Record and assess AEs, concomitant medications, and therapies
- WI-NRS to be entered by subject via Trialogics web portal. Review Subject Symptom Log and Subject Medication Log and collect for filing in source records
- Retrieve e-diary
- Retrieve the 14-day SOWS, review data and assess need for withdrawal intervention

End of Study Telephone Call (Telephone Contact 9; Week 56, Day 392)

During this telephone contact, the following will be assessed and documented:

- Record and assess AEs, concomitant medications, and therapies

- Ask the subject to verbally report their current WI-NRS score and site staff must enter the reported score into the Trialogics web portal. The recommended question text is: “On a scale of zero to ten, with zero being ‘no itch’ and 10 being the ‘worst imaginable itch’, how would you describe your worst itch experience over the last 24 hours?”

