7. STATISTICAL CONSIDERATIONS AND ANALYSIS

7.2. Derived Variables

7.2.1. Baseline

The baseline WI-NRS value is calculated as the arithmetic mean of the WI-NRS values (minimum of 5 required) taken for eligibility review by site at the time of randomization. The Trialogics original average of the WI-NRS will be used as the baseline for all analysis. For all other efficacy and safety variables, baseline is defined as the last non-missing evaluation (including repeated and unscheduled assessments) taken prior to or on the first dose of study medication.

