7.2.7. Visit Window Definitions

Windowing is applicable to efficacy and safety endpoints, except for WI-NRS and SOWS for reporting purposes.

	BL*	Week 2	Week 6	Week 10	Week 14 **	Week 16	Week 20	Week 24	Week 28	Week 32	Week 36	Week 44	Week 52	Week 54	Week 56
Scheduled Day	1	14	42	70	98	112	140	168	196	224	252	308	364	378	
ItchyQoL	Day 1		22 to 56	57 to 84	85 to (titration start day-1)		titration start day to 154	155 to 182	183 to 224		225 to 280	281 to 336	>=337		
PAS and IGA-PN	Day 1			29 to 84	85 to (titration start day-1)		titration start day to 154	155 to 182	183 to 210	211 to 238	239 to 280	281 to 336	>=337		
PBI-P	Day 1			29 to 84	85 to (titration start day-1)		titration start day to 168		169 to 210	211 to 238	239 to 280	281 to 336	>=337		
Sleep Scale	Day 1		22 to 56	57 to 84	85 to (titration start day-1)		titration start day to 154	155 to 182	183 to 224		225 to 280	281 to 336	>=337		
Vital Signs	Day 1	8 to 28	29 to 56	57 to 84	85 to (titration start day-1)	titration start day to 126	127 to 154	155 to 182	183 to 210	211 to 238	239 to 280	281 to 336	337 to 371	>=372	
Clinical lab	Day 1	8 to 28	29 to 70		71 to (titration start day-1)				106 to 252			253 to 336	337 to 371	>=372	
Urinalysis	Day 1								99 to 280				>=281		

* If a Day 1 value is missing, then the last screening value is used as the baseline value.

** In the Week 14 column, the end of the window applies to subjects who go on to enter the open-label period. For subjects who don't enter the open-label period, the end of the window is 14 days later than that displayed in the column.

Statistical Analysis Plan (SAP)

Note: ECG windowing will be established by ERT, who will perform ECG analyses.

If two or more observations fall into the same window, the observation closest to the scheduled day will be used in the analysis. If there is a tie, the later observation will be used.

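### For subjects who skip the extension, the Week 14 WI-NRS forward search has no end, so off-drug scores can enter the primary endpoint ahead of Days 89-91

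*SAP*

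**What the plan says.** SAP 7.3.1 has two cases. Case 1 covers subjects whose Week 14 visit is on or after Study Day 98. It works in this order:

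1. "Use all values in the period Study Day 92 through Study Day 98", and average them if there are at least five.
2. If there are fewer than five, add "any available values in the range from Study Day 99 till titration begins that will bring the total to 5 values". Scores recorded once titration has started are barred. If more are found than needed, those nearest Day 98 are taken.
3. The look-back comes last and covers Days 89-91: "If there are still less than 5 values, continue to use any available values in the first 3".

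Case 2 (visit before Day 98) has no forward search.

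SAP 7.2.7 treats subjects who do not go on to the open-label period separately: for them "the end of the window is 14 days later than that displayed in the column". Its opening sentence, however, takes WI-NRS out of the windowing.

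Protocol 11.2.1 ends daily diary recording at the Week 14 visit. Protocol 9.1.3.6 still collects WI-NRS after drug is stopped. The Last Visit, two weeks after the Off-Treatment visit, has a portal entry. For the End of Study call, four weeks after stopping, the instruction is: "Ask the subject to verbally report their current WI-NRS score and site staff must enter the reported score into the Trialogics web portal".

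Response is a fall of at least 4 points from baseline to Week 14.

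**The concern.** The forward search has an evident purpose: to pick up diary scores when the Week 14 visit runs a day or two late. For subjects who go on to the extension, the start of titration closes it. For subjects who do not, nothing closes it. The remaining scores after Day 98 then come from contacts made after drug has stopped, and step 2 places them ahead of the Day 89-91 scores in step 3.

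This derivation decides responder status on the primary endpoint. A programmer who follows the text would use the Day 112 and Day 126 scores. One who leaves them out would be making an unwritten choice about the primary endpoint.

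**Working it through.** The plan gives no figure on this point, so there is none to reproduce. The check follows the rule through for a subject who completes 14 weeks, stops drug and declines the extension.

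**Which scores exist**

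- Week 14 visit and last dose: Day 98.
- Last Visit: 98 + 14 = Day 112 (Protocol 9.1.3.6).
- End of Study call: 98 + 28 = Day 126 (Protocol 9.1.3.6).
- Daily diary: none after the Week 14 visit (Protocol 11.2.1).
- Start of extension titration: does not occur, so step 2 has no upper limit.

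With four core scores, the rule takes Day 112 fifth. With three, it takes Days 112 and 126. In neither case does it reach Days 89-91.

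**Effect on the mean**

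Let x be the on-drug mean, y the mean of the off-drug scores, k the number of off-drug scores used, and B the baseline. With five scores in total:

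Week 14 mean = ((5 - k)x + ky)/5 = x + k(y - x)/5.

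An on-drug responder (x ≤ B - 4) becomes a non-responder when k(y - x)/5 > (B - 4) - x.

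**Examples.** All scores are assumptions: B = 8, x = 3.5, Days 89-91 recorded at 3.5. If the search stops at Day 98, every row gives a mean of 3.5 and a change of -4.5, a responder.

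| Core scores | Off-drug scores taken | Mean as written | Change | Status |
|---|---|---|---|---|
| 4 | Day 112 = 8 | (4×3.5 + 8)/5 = 4.4 | -3.6 | non-responder |
| 3 | Day 112 = 6, Day 126 = 7 | (3×3.5 + 6 + 7)/5 = 4.7 | -3.3 | non-responder |
| 4 | Day 112 = 6 | (4×3.5 + 6)/5 = 4.0 | -4.0 | responder |

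The margin here is (8 - 4) - 3.5 = 0.5. One off-drug score changes the status only if y - 3.5 > 2.5, so y > 6. Two change it if 2(y - 3.5)/5 > 0.5, so their mean must exceed 4.75.

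The formula works in both directions. If y is below x, the mean falls by k(x - y)/5, and a non-responder close enough to the threshold becomes a responder.

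**Who is exposed**

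All of the following must hold: a Week 14 visit on or after Day 98, fewer than five scores in Days 92-98, too few scores between Day 99 and a late visit to reach five, no extension titration, and a Last Visit or call after Day 98. The documents give no count of such subjects.

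**The case against.** The strongest reply is that the text should be read in context. SAP 7.3.1 describes daily double-blind diary entry and a seven-day average. The Last Visit and the call are separate contacts, and the call is a verbal report keyed in by staff. On that reading, pooling them is a possible literal result, not something the plan sets out to do. It is true that the documents do not show an intention to pool. But the rule admits any available score, limits it by neither source nor treatment status, and names one stop that these subjects never reach. SAP 7.2.7 shows that the need for a separate window end was recognised for other instruments.

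The second reply is scope, and it stands. Early stoppers mostly fall outside the mechanism. Someone off drug before about Day 70 normally has the call by Day 98 (70 + 28 = 98). For anyone who stopped before Day 89, Days 89-91 are off drug too. If such subjects have off-drug scores in Days 92-98, that is a separate estimand question. Scores on Days 99-100 from a late visit also come before Day 112. What is left is mainly completers with sparse diaries who decline the extension.

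A reader might infer that the rule biases the trial toward no effect, because itch would return after NAL ER and not after placebo. The documents do not support that. They contain no data on itch after stopping. Placebo subjects also improve: Protocol 10.6.4 reports an early decline in both TR03 groups, and Protocol 13.1 assumes a 25% placebo response, so placebo responders can worsen as well. Subjects off drug may start other anti-itch treatment, which would lower their scores. Rates of declining the extension by arm are unknown.

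A reader might also attach the lack of a minimum count at Week 14, set against "minimum of 5 required" at baseline. That is a separate matter. A missing minimum does not let off-drug scores in. The baseline minimum is tied to eligibility, Weeks 2, 6 and 10 have no minimum either, and imposing one discards observed data.

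**Conclusion.** The point holds as a fault in a stated rule. As written, Case 1 leaves the forward range open for subjects who never start extension titration and ranks off-drug scores above Days 89-91. This can change responder status on the primary endpoint, by 0.9 points (4.4 against 3.5) or 1.2 points (4.7 against 3.5) in the two assumed examples where status changes. In the third example it does not change.

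The textual gap is certain. Its practical weight is not. The scores are assumed, the number of subjects is unknown and likely small, and the sign of any bias is undetermined. The point should be corrected because the rule bears on the primary endpoint and the repair is cheap, not because a material distortion has been shown. Whether to require five scores at Week 14 is an optional choice and not part of this conclusion.

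**What to change.** In SAP 7.3.1 Case 1:

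1. End the forward range at the earlier of the Week 14 visit date and the day before extension titration starts.
2. State that WI-NRS scores from the Last Visit and the End of Study call are not used for Week 14.
3. Then look back to Days 89-91, as now.

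This keeps the use of diary scores when the visit is late. Extending the 14-day allowance in SAP 7.2.7 to WI-NRS would not be enough: counted from Day 98 it ends on Day 112, which still admits the Last Visit.

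The cost is a change of wording and a small programming edit. A few sparse-diary subjects will have a mean based on fewer scores. With one core score and no later diary entry, at most 1 + 3 = 4 remain; with none, at most 3; and some may have no score at all. For those with none, the SAP should say how they are classified, because Protocol 13.4.6.1 counts a missing Week 14 value as non-response while the SAP's primary analysis leaves it missing.

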7.3.2. ItchyQoL Total Score (ItchyQoL)

The ItchyQoL consists of 22 pruritus-specific items measuring how pruritus affects subjects' QoL in the area of symptoms related to the itch condition (6 questions), functional limitations (7 questions), and emotions (9 questions). The subject scores each question never = 1, rarely = 2, sometimes = 3, often = 4, all the time = 5. The ItchyQoL must be administered at the site under supervision by trained and authorized study staff, strictly adhering to administration instructions.

The ItchyQoL total score will be obtained as the sum of the 22 items. For each subscale (symptoms, functional limitations, emotions) of ItchyQoL, if one item within a subscale is missing, the median of remaining items within that subscale will be used to impute the missing value. If more than 1 item within a subscale is missing, that subscale and the ItchyQoL total score will be set to missing.

7.3.3. PBI-P

Before therapy, the subject fills in the PBI-P questionnaire as to the individual importance of treatment objectives. During and after therapy, the subject completes a matched "on-treatment" questionnaire and rates the extent to which the treatment objectives have been achieved. The instrument consists of 27 multiple choice questions that can be answered "not at all", "somewhat", "moderately", "quite", and "very". The PBI-P must be administered at the site under supervision by trained and authorized study staff, strictly adhering to administration instructions⁴.

Part 1: Patient Needs Questionnaire (PNQ). The PNQ consists of the “treatment goal” items. Each item has 5 categories: not at all (0), somewhat (1), moderately (2), quite (3), and very (4). PNQ is analysed descriptively. The analysis consists of the following:

- means and standard deviations of all items (“does not apply to me” is coded as 0 for this single-item analysis of the PNQ)
- for each item the percentage of the response “does not apply to me”
- for each item the percentage of responses with high agreement (quite or very)
- percentage of missing values

Part 2: Patient Benefit Questionnaire (PBQ). The PBQ consists of the “benefit” items measuring the extent to which the treatment goals have been achieved. It is analysed descriptively. The analysis consists of the following:

- means and standard deviations of all items (“did not apply to me”) is treated as missing here)
- for each item the percentage of the response “did not apply to me”
- for each item the percentage of responses with high agreement (quite or very)
- percentage of missing values

The PBI-P global score may only be computed if the subject has provided valid data on importance (PNQ) and benefit (PBQ) for at least 75% of the respective treatment goals, that is, for at least 21 of the 27 items. The responses “does/did not apply” and “question answered” are considered valid values when counting the number of non-missing responses.

The PBI-P global score is computed for each subject according to the following algorithm.

Identify the subjects who have 21/27 needs answered at baseline & 21/27 of the benefits questions answered at each visit. For this assessment 0 & 5 are considered non-missing.

PBI-P Global Score:

Individual PNQ (‘Patient Needs’ or ‘Importance’) scores are in the SDTM data set QS. (QS.QSTESTCD.PBIP101 to QS.QSTESTCD.PBIP127).

Individual PBQ (‘Patient Benefit’ or ‘Benefit’) scores are in the SDTM data set QS. (QS.QSTESTCD.PBIP201 to QS.QSTESTCD.PBIP227).

1. Determine individual baseline PNQ scores.

2. Count PNQ scores, where individual score is from 1 to 4, as PNQ count.
3. Sum PNQ scores, where individual score is from 1 to 4, as PNQ sum.
4. Merge PBQ score at visit with corresponding baseline PNQ scores, creating item pairs. (e.g., merge PBIP101 with PBIP201) by subject-visit.
5. For each item pair, if both PNQ and PBQ score is 1 to 4, multiply PNQ*PBQ as calculated raw score.
6. Sum calculated raw scores as PBQ sum.
7. If PNQ count ≥ 21 , calculate and output PBI-P Global Score as (PBQ sum/PNQ sum).

However, for the score calculation, both “does/did not apply” and “question unanswered” will be treated as missing values. The global score will be calculated using only those items pairs (i.e., importance item and benefit item) for which the subject has given a response other than “does/did not apply” in both PNQ and PBQ. That is, importance items for which the corresponding benefit item has been rated as “does/did not apply” or “not at all” (or vice versa) will not be included in the sum of needs (i.e., the denominator in the algorithm).

The interpretation of data includes the distribution characteristics of PBI-P (e.g., mean and standard deviation) and the proportion of subjects with $PBI-P \geq 1$, $PBI-P \geq 2$, $PBI-P \geq 3$. Subjects with $PBI-P \geq 1$ are considered as having at least minimum patient-relevant treatment benefit (based on pilot studies).

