APPENDIX 2 PATIENT BENEFIT INDEX, PRURITUS VERSION

PBI-P – Patient Benefit Index, pruritus version**Importance of Treatment Goals**

With the help of the following questions, we'd like to know how important the goals mentioned below are to you personally in the **current treatment** of your skin disease.

For each of the following statements, please mark **how important** this treatment goal is to you.

If a statement does not apply to you, for example because you are not experiencing pain, please mark "*does not apply to me*".

As a result of therapy, how important is it for you to ...

	not at all	somewhat	moderately	quite	very	does not apply to me
1 ...be free of pain						
2 ...be free of itching						
3 ...no longer have burning sensations on your skin						
4 ...be healed of all skin defects						
5 ...concentrate better						
6 ...be less nervous						
7 ...be able to wear all types of clothing						
8 ...be able to bathe and shower normally						
9 ...sleep better						
10 ...feel less depressed						
11 ...experience greater enjoyment of life						
12 ...have no fear that the disease will get worse						
13 ...lead a normal everyday life						
14 ...be more productive in everyday life						
15 ...be less of a burden to relatives and friends						
16 ...engage in normal leisure activities						
17 ...be able to lead a normal working life						
18 ...be able to have more contact with other people						
19 ...be more comfortable showing yourself in public						
20 ...be less burdened in your partnership						
21 ...be able to have a normal sex life						
22 ...be less dependent on doctor and clinic visits						
23 ...need less time for daily treatment						
24 ...have fewer out-of-pocket treatment expenses						
25 ...have fewer side effects						
26 ...find a clear diagnosis and therapy						
27 ...have confidence in the therapy						

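### SAP 7.3.3 sets two incompatible conditions for a PBI-P global score, so a complete form with seven or more importance items marked 'not at all' or 'does not apply' meets one and fails the other

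*SAP*

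**What the plan says.** SAP Section 7.3.3 describes the questionnaire ("The instrument consists of 27 multiple choice questions") and codes the responses "not at all (0), somewhat (1), moderately (2), quite (3), and very (4". It permits a global score only when both questionnaires, importance (PNQ) as well as benefit (PBQ), are sufficiently complete. The threshold on each is "for at least 75% of the respective treatment goals, that is, for at least 21 of the 27 items". Responses of 'does/did not apply' are valid for that count. Just before the numbered steps it tells the programmer: "Identify the subjects who have 21/27 needs answered at baseline & 21/27 of the benefits questions answered at each visit". It adds: "For this assessment 0 & 5 are considered non-missing". Code 0 is 'not at all'. The SAP does not define code 5, and I read it as 'does/did not apply'.

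The numbered steps follow. Step 2 is "Count PNQ scores, where individual score is from 1 to 4, as PNQ count". Step 7 makes output conditional on that count being at least 21, and then says "calculate and output PBI-P Global Score as (PBQ sum/PNQ sum".

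The paragraph after the steps treats 'does/did not apply' as missing, but only for calculating the score.

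The form invites this response. Protocol Appendix 2 says "If a statement does not apply to you, for example because you are not experiencing pain, please mark" and names the 'does not apply to me' box.

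**The concern.** Codes 0 and 5 count towards the 21 in the eligibility text and do not count towards the 21 in step 7. Both instructions cannot be followed for the same subject, and two programmers could derive different sets of scored subjects from this section.

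If step 7 is followed, the proportion with PBI-P of at least 1 at Week 14 describes only subjects who rated at least 21 goals as of some importance, or else counts completed forms as unscored. The SAP does not say how an unscored subject enters that proportion. The non-responder rule in SAP Section 8.6.3 is given for the logistic-regression endpoints listed there, and PBI-P is not among them. The PBI-P mean and the proportions at 2 or more and 3 or more depend on the same step.

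**Working it through.** **Threshold.** 0.75 × 27 = 20.25, rounded up to 21. This reproduces the SAP's figure, so the number is right. The conflict is over which responses count towards it.

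**When the two conditions part.** On a complete importance form, the step 2 count is 27 minus the number of items coded 0 or 5. It falls below 21 when that number is 7 or more, since 27 − 7 = 20.

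**Worked cases.** Each rated goal has importance 4 and benefit 3, so it adds 4 × 3 = 12 to the PBQ sum and 4 to the PNQ sum. Every rated goal has a benefit rating, so the choice of denominator does not affect these cases.

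| Case | Importance items answered | Items rated 1–4 | Stated rule | Step 7 |
|---|---|---|---|---|
| A: 20 rated, 7 'does not apply' | 27 | 20 | met; 240/80 = 3.0 | no score |
| B: 20 rated, 7 'not at all' | 27 | 20 | met; 240/80 = 3.0 | no score |
| C: 21 rated, 6 'does not apply' | 27 | 21 | met; 252/84 = 3.0 | 3.0 |
| D: 21 rated, 6 blank | 21 | 21 | met; 252/84 = 3.0 | 3.0 |

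The benefit form is complete in A to C and has 21 answers in D. D leaves six items blank and is scored. A and B answer everything and are not. Under the stated rule A and B would count as responders at the threshold of 1.

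**How many subjects.** Neither document gives item response rates. As an illustration, let each importance item be coded 0 or 5 with the same probability q, independently. The share of complete forms that lose their score is P(X ≥ 7), with X ~ Binomial(27, q):

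| q (assumed) | Expected items coded 0 or 5 (27q) | P(X ≥ 7) |
|---|---|---|
| 5% | 1.35 | 0.0003 |
| 10% | 2.70 | 0.0147 |
| 15% | 4.05 | 0.0986 |
| 20% | 5.40 | 0.2866 |
| 25% | 6.75 | 0.5292 |

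The share moves from almost none to about half over a plausible range of q. In practice neither independence nor a common rate will hold exactly.

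**The case against.** **The eligibility sentence is a filter that runs before step 1.** That is a fair reading, but it does not remove the conflict. Cases A and B pass the filter with 27 of 27 answered and then fail step 7.

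**'Does not apply' is meant to be missing.** The SAP says so for the score calculation, which concerns the sums. For the eligibility count it says the opposite.

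**The stated rule is only a necessary condition, so step 7 may add a second minimum.** This is logically possible. But step 7 reuses the same 21 without saying that it is a further requirement, and nothing in the section explains one. A drafting slip is more likely.

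**Consequences are limited.** This stands. PBI-P is an 'other' secondary endpoint. Protocol Section 13.4.6.2 plans only counts and percentages for it, and it is last in the testing order of the SAP's multiplicity section.

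A reader might infer three stronger points, and the documents support none of them:

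- *Subjects with few benefit answers could be scored, because step 7 checks only importance.* The sentence before step 1 already requires 21 of 27 benefit answers at the visit.
- *Many subjects will lose their score, for example the retired or single.* Appendix 2 does list goals that need not apply to everyone, such as pain, burning, working life, partnership, sex life, out-of-pocket expenses and side effects. That is exactly seven, and being retired or single bears on only some of them. The documents do not show how often seven would be reached.
- *The arm comparison is biased.* Step 2 uses importance answers given at baseline, before treatment, so this exclusion cannot be driven by treatment.

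**Conclusion.** Section 7.3.3 is wrong as written and should be corrected. Its eligibility rule and steps 2 and 7 give different answers for any subject who meets the answered-item rule on both forms but has fewer than 21 importance items rated 1 to 4. On complete forms this means seven or more importance items coded 0 or 5. The conclusion rests on reading code 5 as 'does/did not apply'; the conflict over code 0 does not need that reading.

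The size is unknown. The illustrative range of 1.5% to 53% of complete forms depends entirely on assumed rates of 10% to 25% per item and on independence. The effect is fewer scored subjects, a population tilted towards those with many stated needs, and an ambiguous derivation for one lower-ranked endpoint.

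**What to change.** In step 7, replace the condition on the PNQ count with the SAP's own rule: at least 21 importance items answered at baseline and at least 21 benefit items answered at the visit, with codes 0 to 5 counted as answered. Define code 5 explicitly. Keep the 1 to 4 restriction for the sums only. Set the score to missing when the PNQ sum is zero, because the answered-item rule would admit a subject who coded every importance item 0 or 5 and for whom the ratio is undefined. State how subjects without a score enter the Week 14 proportion.

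The cost is a few lines of SAP text and one changed condition in the derivation program. There is a small downside: some scores will rest on few item pairs, so report the number of scorable pairs per subject by arm. Settle this before unblinding. If that has passed, state which condition was used and show the result under both.

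If the authors did intend a minimum of 21 goals rated 1 to 4, the eligibility text should say so and give the reason.
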